8.5. Treatment discontinuation

Trial treatment should be permanently discontinued if a patient experiences any of the following:

- disease progression whilst on trial
- an immune-related AE that does not resolve within 12 weeks of last dose of IMP
- treatment with corticosteroids cannot be reduced to ≤ 10 mg prednisolone or equivalent per day within 12 weeks
- Any grade 4 IMP related AE or laboratory abnormality apart from the following:
 - Grade 4 neutropenia <7 days (G-CSF may be instituted, and continued until neutrophils exceed $1.5 \times 10^9/L$, as per institutional policy)
 - Grade 4 lymphopenia
 - Grade 4 amylase abnormalities that are not associated with clinical symptoms
 - Grade 4 drug-related endocrinopathy AEs which are adequately controlled with physiologic hormone replacement
 - Electrolyte abnormalities that can be corrected and are not felt to be a cause for clinical safety concern.
- Grade 2 infusion related reaction (pembrolizumab related) for a second time despite receiving premedication
- Any grade 3 or 4 infusion related reaction (pembrolizumab related)

In instances where patients discontinue treatment, both pembrolizumab and rituximab should be discontinued. Patients will continue to be followed up in line with the protocol (see section 8.11).

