8.2. Treatment Summary

Patients with relapsed/refractory WM meeting the eligibility criteria will be fully registered into the study. Patients will be treated with rituximab 375mg/m² IV infusion and pembrolizumab 200mg IV infusion on a 3 weekly cycle, for a maximum of 18 cycles on the following days:

- Cycle 1:
 - Rituximab 375mg/m² - days 1, 8 and 15
 - Pembrolizumab 200mg - day 2
- Cycle 2:
 - Rituximab 375mg/m² - day 1
 - Pembrolizumab 200mg - day 1
- After cycle 2:
 - Rituximab 375mg/m² - 12 weekly on day 1 (cycles 6, 10, 14 & 18)
 - Pembrolizumab 200mg - day 1 of every cycle

Treatment will continue until cycle 18 unless disease progression or discontinuation due to toxicity or any other cause (whichever occurs sooner). Patients who experience

disease progression at any point during the trial will have the study therapy ceased and be managed as per standard of care at their institution.

Where both rituximab and pembrolizumab are delivered on the same day, rituximab should be administered first.

See diagram below for visual representation.

Cycle	1	2	3	4	5	6	7	8	9	10	11	12	13	14	15	16	17	18
Day	1	2	8	15	1	1	1	1	1	1	1	1	1	1	1	1	1	1
Rituximab (375 mg/m ² IV)	X		X	X	X			X			X			X				X
Pembrolizumab (200mg IV)		X			X	X	X	X	X	X	X	X	X	X	X	X	X	X

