8.3.3. Administration for IgM flare

Prior to the first cycle, if the total IgM is >40, pre-emptive plasmapheresis is recommended to get total IgM <40 and prevent IgM flare – defined as a >25% increase in total IgM. This phenomenon has been associated with single agent rituximab therapy in this setting, and can be associated with symptomatic hyperviscosity and/or escalation of WM related symptoms (e.g. neuropathy).

See section 8.4.6 for further details on IgM flare management.

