8.4.6. IgM flare

If there are any clinical or laboratory concerns about IgM flare in the first 2 cycles, plasmapheresis/other supportive care may be instituted and the subject may remain on trial treatment.

If at any timepoint after the end of cycle 2 plasmapheresis is required for symptomatic relief of IgM flare (or for any other reason), then the patient will have to cease study therapy and be managed as per standard of care at their institution.

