9.2.1. Assessments prior to each cycle of treatment

The following assessments should be performed within 3 days prior to each cycle:

- Clinical examination: physical examination (including assessment of lymph node, liver and spleen size)
- Concurrent medication assessment
- Adverse event assessment
- Observations: pulse, temperature, blood pressure, oxygen saturations
- Weight
- Assessment of ECOG performance status (see appendix 3)
- Full blood count (including red blood cell (RBC), haemoglobin (Hb), white blood cell (WBC) absolute neutrophil count (ANC), absolute lymphocyte count (ALC), haematocrit and platelets)
- Biochemistry (including bicarbonate, uric acid, albumin, alkaline phosphatase (ALP), alanine/aspartate transaminase (ALT/AST), total bilirubin, calcium, creatinine, potassium, sodium, glucose, urea, and estimated glomerular filtration rate (eGFR), U&E, liver function tests (LFT), and amylase)
- Electrocardiogram (ECG)
- Serum IgM, IgG and IgA
- Serum paraprotein
- Serum immunofixation (only to be performed if paraprotein not detectable)
- TSH, glucose and ACTH tests
- Highly sensitive urine or serum pregnancy test in women of childbearing potential (WOCBP)

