9.3. Assessments after Disease Progression

Following disease progression patients will be assessed at 5 months (+4 weeks) after the date of treatment discontinuation, over the phone or at a standard hospital visit for the purposes of:

- Adverse event assessment

Patients are then followed up for the trial annually from the date of progression for the following:

- Remission status assessment (investigations as per local protocols)

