12.5. Urgent events

The following events must be collected and reported as urgent events between start of treatment and the end of the trial. They must be reported on the relevant CRF and emailed to UCL CTC within the timelines stated. If the event meets a definition of an SAE, an SAE report must also be submitted as per Section 12.2.2.

Event	Description	Form required	Timeframe
Death	Death from any cause (reportable at any point while the patient is enrolled onto the trial).	Death form	Within 24 hours of becoming aware of the death
Disease progression	Progression of WM, confirmed by standard local investigations (if local investigations are inconclusive, UCL CTC should be contacted for advice)	Disease progression form	Within 72 hours of becoming aware of confirmed progression

All Urgent Events must be reported by emailing a completed Urgent Event Form to UCL CTC within the timeframes specified above of becoming aware of the event

Email: [contact]

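### Nothing states that an IgM flare in cycles 1–2 is not progression, so a patient whom 8.4.6 keeps on treatment can meet the IgM criterion for a permanent stop

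*Combined protocol and SAP*

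**What the plan says.** **Flare.** Section 8.3.3 describes IgM flare as "defined as a >25% increase in total IgM", associates it with single-agent rituximab, and notes that it can bring hyperviscosity or worsening WM symptoms. It does not name the value from which the increase is measured. Section 8.4.6 says that if there are flare concerns "in the first 2 cycles, plasmapheresis/other supportive care may be instituted and the subject may remain on trial treatment".

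**Progression.** Appendix 3 gives two criteria, either of which is enough: an IgM increase of at least 25% from the lowest nadir, or clinical progression attributable to the disease. An IgM progression should be confirmed by a second measurement, ideally in the same cycle. Footnote c asks that plasmapheresis be considered when the nadir is fixed. There is no early window and no mention of flare.

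**Consequence of progression.** Section 8.2 says that patients with "disease progression at any point during the trial will have the study therapy ceased". Section 8.5 states: "Trial treatment should be permanently discontinued if a patient experiences any of the following", and lists "disease progression whilst on trial" first. Section 9.3 then applies: "Following disease progression patients will be assessed at 5 months (+4 weeks) after the date of treatment discontinuation", for adverse events only, with annual remission status after that. In 17.2.1, a missing week-24 response in a patient who has progressed or died counts as non-response. Section 17.2.2 counts progression as a PFS event.

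**The concern.** Flare is an expected early effect of one of the two trial drugs, and the protocol plans for it. Yet the response appendix, applied as written, would label a confirmed flare as progression. Section 8.4.6 tells the site that the patient may continue. It does not say what to put on the progression form, or how the rise enters the response and PFS analyses.

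At stake is consistent classification in the primary endpoint and in PFS. Two sites with identical patients could record opposite outcomes, both with support in the text, and the primary endpoint is judged against a fixed cut-off of 23 responses in 42 patients (17.1).

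**Working it through.** **1. Do the two definitions overlap?** Let B be the pre-treatment IgM and N the lowest nadir. Two assumptions are needed: flare is measured from B, and the pre-treatment value counts towards the nadir, so N ≤ B.

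- Flare (8.3.3): IgM > 1.25 × B.
- Progression by IgM (Appendix 3): IgM ≥ 1.25 × N, confirmed.
- Since N ≤ B, IgM > 1.25 × B implies IgM > 1.25 × N.

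So every confirmed flare meets the IgM criterion. For example, take a patient starting at 40, the level 8.3.3 uses for pre-emptive plasmapheresis. Flare is any value above 1.25 × 40 = 50. With N = 40, progression is any value of 50 or more.

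**2. Would the rise be seen?** Section 9.2.1 says: "The following assessments should be performed within 3 days prior to each cycle", and serum IgM is on that list. With 3-week cycles, the draws before cycles 2 and 3 fall at about weeks 3 and 6. Section 12.5 sets the deadline for the progression form: "Within 72 hours of becoming aware of confirmed progression".

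**3. What follows from each label?**

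| | Recorded as progression | Recorded as flare |
|---|---|---|
| Treatment | Permanent stop (8.2, 8.5) | May continue (8.4.6) |
| Week-24 IgM | Not scheduled (9.3) | Scheduled (9.2.2) |
| Primary endpoint | Missing and progressed: non-responder (17.2.1) | Judged on the week-24 value |
| PFS | Early event | No event |

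A mixed case is possible but needs a departure from 8.2 and 8.5: progression is recorded, treatment continues, and the patient responds. That patient would be both a responder and an early PFS event.

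**4. How much could it matter?** Reproducing the design in 17.1 first, with n = 42 and a cut-off of 23:

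- P(X ≥ 23 | p = 0.40) = 0.0375.
- P(X ≥ 23 | p = 0.60) = 0.803.

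Both agree with the stated one-sided 0.05 and 80% power.

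Now suppose that k patients are stopped for a flare recorded as progression and so cannot be responders, and that response is unrelated to flare. Then X ~ Bin(42 − k, 0.60), with expected responders 0.60 × (42 − k). The documents give no flare rate, so k is purely an assumption.

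| k | Expected responders | P(X ≥ 23) |
|---|---|---|
| 0 | 25.2 | 0.803 |
| 2 | 24.0 | 0.689 |
| 4 | 22.8 | 0.544 |
| 8 | 20.4 | 0.233 |

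The expected count falls below 23 once k exceeds 42 − 23/0.60 = 3.67, that is, from four patients (4/42 = 9.5%).

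**The case against.** **The specific rule governs.** Section 8.5 never mentions flare. The protocol treats flare as a separate entity with its own dosing rule, and permission to continue would be empty if the same rise were already progression. Investigators must have experience of WM (4.1.1). This is the natural reading for dosing, and it stands. It does not reach the progression form, PFS or the missing-response table, none of which mentions flare.

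**Central advice is available.** Appendix 3 sends sites to the TMG, and 12.5 to UCL CTC, when local investigations are inconclusive. That helps with doubtful cases, including uncertainty over whether symptoms are due to the disease. A confirmed rise above the written threshold is not inconclusive on the protocol's own terms.

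**Timing.** Section 9.2.2 applies the response criteria at 12 weeks, 24 weeks and 1 year, and cycles 1–2 end at about week 6. No text requires Appendix 3 to be applied to a week 3 or week 6 value. But 8.2 stops treatment for progression at any point, and the draws are made, so early progression is not ruled out either.

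**Size.** The values of k are arbitrary. Each lost patient requires a confirmed flare that a site records as progression despite 8.4.6. That is right, and the table in the working is an illustration, not an estimate. The modelled error also only removes responders, so it does not raise the 0.0375 false-positive rate.

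**Conclusion.** The gap is real and should be fixed. Confidence is moderate, because the conflict arises by inference through the Appendix 3 definition of progression. It rests on flare being measured from the pre-treatment value, on that value counting towards the nadir, and on the rise being confirmed. The size is unknown. If sites follow 8.4.6 and record no progression, nothing is lost.

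Three stronger readings might be inferred, and the documents do not support them.

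- **That 8.5 directly orders a stop for flare.** It does so only if the rise is classed as progression.
- **That the table in the working gives a worst case.** It has no ceiling on k, and the loss would be larger if flare patients respond more often than others.
- **That 8.5 broadly contradicts 8.4.2 on grade 4 thyroid events.** Section 8.5 exempts grade 4 endocrinopathy that is adequately controlled on hormone replacement, and replacement is what 8.4.2 prescribes for hypothyroidism. For grade 4 hyperthyroidism, 8.4.2 says to withhold or stop, not to continue.

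A minor mismatch remains on thyroid events. Grade 4 hyperthyroidism is treated with beta-blockers or thionamides, which are not hormone replacement. Section 8.5 therefore forces a stop where 8.4.2 leaves withholding to discretion. For grade 4 hypothyroidism that is not adequately controlled, 8.4.2 says continue and 8.5 says stop. Neither changes how the primary endpoint is defined or counted.

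**What to change.** 1. In Appendix 3, state that an IgM rise in cycles 1–2 attributed to flare, including flare-related symptoms, is not progression, and that the TMG should be asked where attribution is uncertain.
2. In the same place, name the visit from which, and the reference value against which, an IgM rise can count as progression. The clinical team should set both. Name the reference value for flare in 8.3.3 as well.
3. Cross-refer to this rule in 8.2, in the first item of 8.5, in 17.2.1 and in the PFS definition in 17.2.2, so that dosing, response and PFS use one classification.
4. Separately, align 8.4.2 and 8.5 for grade 4 hyperthyroidism and for grade 4 hypothyroidism not controlled on replacement.

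The cost is a protocol wording amendment, a note to sites and, if the CRFs lack one, an entry to record flare (the CRFs are not among the documents). No visits or tests are added, because IgM is already measured before every cycle.

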AST / ALT elevation or Increased bilirubin	Grade 2	Withhold treatment	
 Administer corticosteroids (initial dose of 0.5- 1 mg/kg prednisolone or equivalent) followed by taper 	
 Monitor with liver function tests (consider weekly or more frequently until liver enzyme value returned to baseline or is stable)
	Grade 3 or 4	Permanently discontinue treatment	
 Administer corticosteroids (initial dose of 1-2 mg/kg prednisolone or equivalent) followed by taper 	

Immune-related AEs	Severity grade CTCAE v5.0	Action taken	irAE management	Monitor and follow-up
Type 1 diabetes mellitus (T1DM) or Hyperglycaemia	Newly onset T1DM or Grade 3 or 4 hyperglycaemia associated with evidence of β -cell failure	Withhold treatment ¹	
 Initiate insulin replacement therapy for participants with T1DM Administer anti-hyperglycaemic in participants with hyperglycaemia 	
 Monitor participants for hyperglycaemia or other signs and symptoms of diabetes.
Hypophysitis	Grade 2	Withhold treatment	
 Administer corticosteroids and initiate hormonal replacements as clinically indicated. 	
 Monitor for signs and symptoms of hypophysitis (including hypopituitarism and adrenal insufficiency)
	Grade 3 or 4	Withhold or permanently discontinue treatment ¹		
Hyperthyroidism	Grade 2	Continue treatment	
 Treat with nonselective beta-blockers (e.g., propranolol) or thionamides as appropriate 	
 Monitor for signs and symptoms of thyroid disorders.
	Grade 3 or 4	Withhold or permanently discontinue treatment ¹		
Hypothyroidism	Grade 2-4	Continue treatment	
 Initiate thyroid replacement hormones (e.g., levothyroxine or liothyroinine) per standard of care 	
 Monitor for signs and symptoms of thyroid disorders.
Nephritis associated with increased creatinine or acute kidney injury	Grade 2	Withhold treatment	
 Administer corticosteroids (prednisolone 1-2 mg/kg or equivalent) followed by taper. 	
 Monitor changes of renal function
	Grade 3 or 4	Permanently discontinue treatment		

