Neurological Toxicities	Grade 2	Withhold treatment	
 Based on severity of AE administer corticosteroids 	
 Ensure adequate evaluation to confirm aetiology and/or exclude other causes
	Grade 3 or 4	Permanently discontinue treatment		
Myocarditis	Grade 1	Withhold treatment	
 Based on severity of AE administer corticosteroids 	
 Ensure adequate evaluation to confirm aetiology and/or exclude other causes
	Grade 2-4	Permanently discontinue treatment		
Exfoliative Dermatologic Conditions	Suspected Steven-Johnson syndrome (SJS), Toxic epidermal necrolysis (TEN) or Drug rash with eosinophilia and systemic symptom (DRESS)	Withhold treatment	
 Based on severity of AE administer corticosteroids 	
 Ensure adequate evaluation to confirm aetiology and/or exclude other causes

Immune-related AEs	Severity grade CTCAE v5.0	Action taken	irAE management	Monitor and follow-up
	Confirmed SJS, TEN or DRESS	Permanently discontinue treatment		
All other immune-related AEs	Persistent Grade 2	Withhold treatment	
 Based on type and severity of AE administer corticosteroids Ensure adequate evaluation to confirm aetiology and/or exclude other causes 	
	Grade 3	Withhold or discontinue treatment based on type of event. Events that require discontinuation include and not limited to: encephalitis and other clinically important irAEs (e.g. vasculitis and sclerosing cholangitis)		
	Grade 4 or recurrent Grade 3	Permanently discontinue treatment		

1. 'Withhold or permanently discontinue treatment' is at the discretion of the investigator or treating physician.

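### After grade 4 hyperthyroidism, the 8.4.2 table lets the investigator withhold and later resume both drugs, while 8.5 requires permanent discontinuation

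*Combined protocol and SAP*

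**What the plan says.** Section 8.5 lists events after which trial treatment is permanently discontinued, and says that both drugs then stop. One item is "Any grade 4 IMP related AE or laboratory abnormality apart from the following", followed by five exceptions: neutropenia lasting under 7 days, lymphopenia, amylase abnormalities without symptoms, correctable electrolyte abnormalities, and "Grade 4 drug-related endocrinopathy AEs which are adequately controlled with physiologic hormone replacement".

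The 8.4.2 table gives event-specific actions for immune-related events attributed to pembrolizumab. For hyperthyroidism at grade 3 or 4 the action is "Withhold or permanently discontinue treatment", and footnote 1 to the table leaves that choice to the investigator or treating physician. The management entry in the same row is "Treat with nonselective beta-blockers (e.g., propranolol) or thionamides as appropriate". The text above the table has withheld treatment resume at grade 1 or 0.

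Section 8.4.1 requires both drugs to be withheld together and sends the reader to 8.5 for full discontinuation details. Section 15.2 gives the same pointer for unacceptable toxicity.

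**The concern.** Two operative dosing sections answer the same clinical question differently. A site working from the table may withhold both drugs after grade 4 hyperthyroidism and give them again on recovery. A site working from 8.5 must stop both for good. For an affected patient the difference is re-exposure to pembrolizumab and rituximab, or none.

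There is also a compliance side. Section 13.1 requires immediate notification of every protocol deviation. Section 14.4 names failure to observe dose-modification rules after an adverse event as an example of possible patient risk, to be escalated urgently and assessed as a possible serious breach. A site that re-doses as the table allows could be recorded as deviating from 8.5, and a monitor has no stated precedence rule by which to decide.

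**Working it through.** No arithmetic beyond a row count applies. The check takes one case, grade 4 pembrolizumab-related hyperthyroidism, through both sections.

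1. **Does the 8.5 grade 4 rule apply?** Yes. The table is for immune-related events associated with pembrolizumab, so relatedness to a trial drug is already met, and the grade is 4.
2. **Does an exception apply?** Four of the five (neutropenia, lymphopenia, amylase, electrolytes) concern other events. The endocrine exception requires adequate control by physiologic hormone replacement. Beta-blockers and thionamides do not replace a hormone. As worded, 8.5 requires permanent discontinuation.
3. **What does the table allow?** Withholding, at discretion, then resumption at grade 1 or 0, subject to the 12-week limits in 8.4.1 and 8.5.
4. **Does other text settle it?** The last row of the table requires permanent discontinuation for "Grade 4 or recurrent Grade 3" events, but it covers only immune-related events without their own row. Footnote 2 in 8.4.4 repeats the endocrine exception, but that section applies to events not in the preceding tables. The pointers in 8.4.1 and 15.2 suggest that 8.5 governs without saying that it overrides the discretion in the table.

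The same test can be run on the rest of the table. It has 12 rows; the exfoliative skin row is ungraded, which leaves 11 with a grade 4 action. Seven of these require permanent discontinuation at grade 4: pneumonitis, diarrhoea/colitis, liver enzymes/bilirubin, nephritis, neurological toxicity, myocarditis, and all other immune-related events. The remaining 11 − 7 = 4 are the endocrine rows:

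| Row | Action at grade 4 | Management listed | Agreement with 8.5 |
|---|---|---|---|
| Hyperthyroidism | Withhold or discontinue, at discretion | Beta-blockers or thionamides | None if treatment is resumed; no hormone replacement is listed |
| Hypothyroidism | Continue, same as grades 2 and 3 | "Initiate thyroid replacement hormones" | Only if the event is adequately controlled on replacement; the row sets no such condition |
| Hypophysitis | Withhold or discontinue, at discretion | Corticosteroids, and "initiate hormonal replacements as clinically indicated" | Only if replacement is given and controls the event |
| Type 1 diabetes / hyperglycaemia | Withhold | "Initiate insulin replacement therapy for participants with T1DM"; an anti-hyperglycaemic for hyperglycaemia | Only if controlled on insulin; an anti-hyperglycaemic need not be hormone replacement |

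So one row conflicts with 8.5 on its face whenever the withhold-and-resume option is used. Three more match it conditionally, on a condition that the table never states.

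**The case against.** The best defence is that the sections can be read together. The hyperthyroidism row pools two grades and includes permanent discontinuation among its options, so an investigator who stops at grade 4 satisfies both texts. Given the pointers to 8.5, discretion could be taken to apply at grade 3 and to end at grade 4. That reading is sensible, but the reader has to supply it: footnote 1 makes the choice discretionary without tying it to grade.

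A second defence is that the table may be right and the exception too narrow. All four endocrine rows avoid mandatory discontinuation at grade 4, and 8.5 itself treats endocrine events separately, which is consistent with an intent to let manageable ones continue. This stands as a possibility, and the sponsor should be able to choose it. It does not rescue the current wording, because the hormone-replacement qualifier appears both in 8.5 and in the 8.4.4 footnote.

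Third, there are safeguards. Re-dosing needs recovery to grade 1 or 0 within the 12-week limit, and 8.4.1 stops or delays dosing when the investigator sees substantial clinical risk. A life-threatening event would be reported as an SAE within 24 hours and reviewed by the chief investigator or a delegate (12.2.2). These lower the chance that a case passes unnoticed. None states which rule applies.

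A reader might go further and infer that hyperthyroidism is the only problem and that the rest of the table fits 8.5. The documents do not support that: listing a hormone replacement is not the same as requiring adequate control on it. Nor does the table compel re-dosing; it permits it.

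**Conclusion.** The inconsistency is real and narrow. It rests on the literal wording of the 8.5 exception and on beta-blockers and thionamides not being physiologic hormone replacement. It is confined to grade 4: at grade 3 the 8.5 grade 4 rule is not engaged. A patient who later becomes hypothyroid and is controlled on replacement might arguably come within the exception, but that is not the management the row describes.

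The number of patients affected cannot be estimated, because the documents give no rate for grade 4 hyperthyroidism; with 42 patients planned it is likely to be very few. A reader might infer that the trial's conclusions are at risk. They are not shown to be: the sample size of 42, the threshold of 23 responses and the planned primary analysis in section 17 do not depend on this rule. Section 8.5 sets a discontinuation criterion for individual patients, not a stopping rule for the trial. The point merits correction because it leaves a patient-level safety instruction contradictory and is cheap to repair.

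**What to change.** - Add one sentence to 8.4.2 stating that 8.5, with its listed exceptions, governs every grade 4 event in the table. This also supplies the missing control condition for the other three endocrine rows.
- Split the hyperthyroidism row: grade 3, withhold or permanently discontinue at the investigator's discretion; grade 4, permanently discontinue per 8.5.
- If the sponsor meant to allow re-dosing after medically controlled grade 4 hyperthyroidism, widen the 8.5 exception and the matching 8.4.4 footnote in explicit terms instead. Without such a statement of intent, the existing 8.5 rule should be the default, since 8.4.1 and 15.2 both refer to it.

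The cost of the default is a small loss of investigator discretion at grade 4 and a wording amendment. If the amendment is classed as substantial, 14.5.1 requires Trial Management Group review before submission, and 18.4 requires ethical and regulatory approval as appropriate. It can be bundled with the next amendment.
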